**Figure 2: Outcome Evaluation Study Design**

**Surveys:**

Investigators will send participants hyperlinks via 5 text messages weekly at the end of weeks 2, 3, 5, 6, and 7 PP. Hyperlinks will lead to a brief questionnaire that participants can complete through a smartphone or tablet. Participants will complete a tablet-based survey in person at their 4 week visit. Participants will receive an emailed hyperlink at the end of week 8 which will lead to a longer questionnaire. A telephone survey will be available as an alternative to the digital questionnaires if desired. Survey questions will address continuation of and satisfaction with breastfeeding, the use of supplemental feeding, types of supplemental feeding being used, use of contraception, and satisfaction with contraception.

At 8 weeks PP, participants will be emailed and requested to complete a more detailed questionnaire eliciting breastfeeding continuation, supplementation amount and type, episodes of lactation support, perception of adequate milk supply, vaginal bleeding patterns, satisfaction with breastfeeding and

contraceptive use, satisfaction with contraception, infant health and well-being, and any new pregnancies and respective pregnancy outcomes if available. Additional potential confounding factors will be explored, such as use of nipple shields, pacifiers, breastmilk expression, and other medications the participant is using. Participants will receive a gift card via text or email link for each completed survey.

Both text and email questionnaires will be sent via a hyperlink that connects to a HIPAA-compliant secure platform that will input the data directly into a REDCap database. Participants who do not have smartphones or email access will be offered participation instead using phone surveys administered by study staff and gift cards will be mailed to these participants.

#### **Breastmilk collection and analysis:**

Women will attend an in-person visit at 4 weeks PP with their infant. Participants will have the option to collect a mid-feeding sample at home with all pumping materials and instructions sent to her home or collect a sterile sample at the visit using a study-provided breast pump. 10 mLs of breastmilk from the collection (either refrigerated sample brought to the visit or collected on-site) will be frozen at the site of the visit at the research site. The milk samples will be frozen at -80 degrees onsite. The lab will use liquid chromatography to assess the composition of breast milk and compare the concentrations of total fat, total protein and carbohydrates including oligosaccharides.

#### **8.2 SAFETY AND OTHER ASSESSMENTS**

A Data Safety and Monitoring Board (DSMB) is not planned for this small pilot study.

#### **8.3 ADVERSE EVENTS AND SERIOUS ADVERSE EVENTS**

##### **8.3.1 DEFINITION OF ADVERSE EVENTS (AE)**

The FDA definition of an Adverse event is any untoward medical occurrence associated with the use of an intervention in humans, whether or not considered intervention-related (21 CFR 312.32 (a)).

##### **8.3.2 DEFINITION OF SERIOUS ADVERSE EVENTS (SAE)**

An adverse event (AE) or suspected adverse reaction is considered "serious" if, in the view of either the investigator or sponsor, it results in any of the following outcomes: death, a life-threatening adverse event, inpatient hospitalization, a persistent or significant incapacity or substantial disruption of the ability to conduct normal life functions, or a congenital anomaly/birth defect. Important medical events that may not result in death, be life-threatening, or require hospitalization may be considered serious when, based upon appropriate medical judgment, they may jeopardize the participant and may require medical or surgical intervention to prevent one of the outcomes listed in this definition.

##### **8.3.3 CLASSIFICATION OF AN ADVERSE EVENT**

###### **8.3.3.1 SEVERITY OF EVENT**

For adverse events (AEs) not included in the protocol defined grading system, the following guidelines will be used to describe severity.

- **Mild** – Events require minimal or no treatment and do not interfere with the participant’s daily activities.
- **Moderate** – Events result in a low level of inconvenience or concern with the therapeutic measures. Moderate events may cause some interference with functioning.
- **Severe** – Events interrupt a participant’s usual daily activity and may require systemic drug therapy or other treatment. Severe events are usually potentially life-threatening or incapacitating. Of note, the term “severe” does not necessarily equate to “serious”.

#### 8.3.3.2 RELATIONSHIP TO STUDY INTERVENTION

All adverse events (AEs) must have their relationship to study intervention assessed by the clinician who examines and evaluates the participant based on temporal relationship and his/her clinical judgment. The degree of certainty about causality will be graded using the categories below. In a clinical trial, the study product must always be suspect.

- **Related** – The AE is known to occur with the study intervention, there is a reasonable possibility that the study intervention caused the AE, or there is a temporal relationship between the study intervention and event. Reasonable possibility means that there is evidence to suggest a causal relationship between the study intervention and the AE.
- **Not Related** – There is not a reasonable possibility that the administration of the study intervention caused the event, there is no temporal relationship between the study intervention and event onset, or an alternate etiology has been established.

OR

- **Definitely Related** – There is clear evidence to suggest a causal relationship, and other possible contributing factors can be ruled out. The clinical event, including an abnormal laboratory test result, occurs in a plausible time relationship to study intervention administration and cannot be explained by concurrent disease or other drugs or chemicals. The response to withdrawal of the study intervention (DE challenge) should be clinically plausible. The event must be pharmacologically or phenomenologically definitive, with use of a satisfactory rechallenge procedure if necessary.
- **Probably Related** – There is evidence to suggest a causal relationship, and the influence of other factors is unlikely. The clinical event, including an abnormal laboratory test result, occurs within a reasonable time after administration of the study intervention, is unlikely to be attributed to concurrent disease or other drugs or chemicals, and follows a clinically reasonable response on withdrawal (dechallenge). Rechallenge information is not required to fulfill this definition.
- **Potentially Related** – There is some evidence to suggest a causal relationship (e.g., the event occurred within a reasonable time after administration of the trial medication). However, other factors may have contributed to the event (e.g., the participant’s clinical condition, other concomitant events). Although an AE may rate only as “possibly related” soon after discovery, it can be flagged as requiring more information and later be upgraded to “probably related” or “definitely related”, as appropriate.
- **Unlikely to be related** – A clinical event, including an abnormal laboratory test result, whose temporal relationship to study intervention administration makes a causal relationship improbable (e.g., the event did not occur within a reasonable time after administration of the

study intervention) and in which other drugs or chemicals or underlying disease provides plausible explanations (e.g., the participant's clinical condition, other concomitant treatments).

- **Not Related** – The AE is completely independent of study intervention administration, and/or evidence exists that the event is definitely related to another etiology. There must be an alternative, definitive etiology documented by the clinician.

#### 8.3.3.3 EXPECTEDNESS

The PI will be responsible for determining whether an adverse event (AE) is expected or unexpected. An AE will be considered unexpected if the nature, severity, or frequency of the event is not consistent with the risk information previously described for the study intervention.

#### 8.3.4 TIME PERIOD AND FREQUENCY FOR EVENT ASSESSMENT AND FOLLOW-UP

The occurrence of an adverse event (AE) or serious adverse event (SAE) may come to the attention of study personnel during study visits and interviews of a study participant presenting for medical care, by communication from the participant to the study team, or upon review by a study monitor.

All AEs including local and systemic reactions not meeting the criteria for SAEs will be captured. Information to be collected includes event description, time of onset, clinician's assessment of severity, relationship to study product (assessed only by those with the training and authority to make a diagnosis), and time of resolution/stabilization of the event. All AEs occurring while on study must be documented appropriately regardless of relationship. All AEs will be followed to adequate resolution.

Any medical condition that is present at the time that the participant is screened will be considered as baseline and not reported as an AE. However, if the study participant's condition deteriorates at any time during the study, it will be recorded as an AE. Changes in the severity of an AE will be documented to allow an assessment of the duration of the event at each level of severity to be performed. AEs characterized as intermittent require documentation of onset and duration of each episode.

At each study visit, the investigator will inquire about the occurrence of AE/SAEs since the last visit. Events will be followed for outcome information until resolution or stabilization.

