## 1 PROTOCOL SUMMARY

### 1.1 SYNOPSIS

Title:	Postpartum progestin-only pill use and breastfeeding study
Study Description:	This study will assess the impact of early initiation (less than one week postpartum) and delayed initiation (4 weeks postpartum) of two types of progestin-only contraceptive pills on maternal, breastmilk, and infant outcomes. This is a placebo-controlled randomized controlled trial enrolling dyads of mothers and their newborn babies. We will explore if the type and timing of initiation of pills is acceptable to the user with minimal side effects, impacts the supply or composition of breastmilk, and/or affects infant growth.
Aims:	Specific Aim: To determine whether the type of progestin used (drospirenone in drospirenone-containing progestin-only pills (d-POPs) vs. norethindrone in norethindrone-containing progestin-only pills (n-POPs)) or the timing of progestin initiation (early vs. delayed) affects: Aim 1a Maternal: the duration of exclusive breastfeeding continuation or the rates and types of breastfeeding supplementation over 8 weeks postpartum. Aim 1b Maternal: the proportion of mothers using progestin-only pills at 8 weeks postpartum. Aim 2 Milk: the composition of breastmilk (fat, protein, carbohydrates) at 4 weeks postpartum. Aim 3 Infant: infant growth (weight, length, and head circumference) from birth to 4 weeks.
Study Population:	Postpartum women who delivered an infant within the previous 7 days
Description of Sites	University of California, San Diego (UCSD)
Enrolling Participants:	
Study Duration:	1 year
Participant Duration:	8 weeks

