The natural PP decline in serum progesterone triggers lactogenesis; therefore, there is theoretical concern that use of progestin-containing contraceptives within the first weeks after delivery could inhibit initiation of breastfeeding or impact establishment of supply or composition of breastmilk. In addition, since progestins have been detected in breastmilk, there is concern about the effect of progestin exposure on early infant growth and development. Most existing studies on PP use of progestins initiated within days of delivery are small and of poor to fair quality, but the available data suggest that there is no effect on onset of lactogenesis, quantity or composition of breastmilk, breastfeeding rates, or infant growth. However, the Centers for Disease Control and Prevention (CDC) Medical Eligibility Criteria (MEC) for contraceptive use cites a paucity of high-quality data for ongoing concerns about the potential effect of progestins on breastfeeding and infant growth and their decision to categorize progestins use in the early PP period as Category 2 (advantages generally outweigh theoretical or proven risks) instead of Category 1 (no restriction). Whether progestin use affects

breastfeeding performance or infant health was identified as a priority research gap by the CDC. High-quality data on the potential effects of the timing of progestin initiation on breastfeeding are urgently needed to inform national and international guidelines on contraceptive use during breastfeeding.

A new progestin-only pill containing drospirenone has benefits compared to traditional norethindrone progestin-only pills, including less reliance on a narrow window of time for pill intake to maintain efficacy, but data on use of this type of progestin in breastfeeding are lacking. Because estrogen-containing contraceptives are contraindicated for a minimum of 21 days PP due to the risk of thromboembolism, and have been associated with decreased breastmilk supply, progestin-only contraception, including progestin-only pills (POPs) are commonly used for contraception among breastfeeding women regardless of time since birth. Approximately 16-20% of PP women who intend to breastfeed choose POPs for contraception following delivery in the U.S, approximately 500,000 women per year.

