### 5.1 INCLUSION CRITERIA

There will be a total of 30 postpartum women enrolled in this study. Participants will need to meet the following criteria:

- Are 18 years of age or older
- Desires to use POPs for 3 months
- Speak English or Spanish
- Had a vaginal or cesarean delivery of a singleton full term ( $\geq 37$  weeks) infant less than 168 hours prior
- Intends to breastfeed exclusively for 6 months

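### Section 8.3 never says that adverse event collection covers the infant, and infant health is a listed survey topic only at week 8

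*Combined protocol and SAP*

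**What the plan says.** **Who is in the trial.** The synopsis (1.1) describes the trial as "enrolling dyads of mothers and their newborn babies". The eligibility and completion sections are about the mother. Section 5.1 says "There will be a total of 30 postpartum women enrolled in this study", its first criterion is "Are 18 years of age or older", and section 4.2 refers to the participant as she.

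**Why the infant matters.** The background (2.2) notes that progestins have been found in breastmilk and that "there is concern about the effect of progestin exposure on early infant growth and development". Section 2.3.3 counts changes in infant growth among the potential risks. The list of known risks in 2.3.1 names none for the infant.

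**How events are found and graded.** Section 8.3.4 says that events may come to light at study visits, through "interviews of a study participant presenting for medical care, by communication from the participant to the study team", or on monitor review. It also requires the investigator to ask about AEs and SAEs at each study visit. The important-medical-event clause in 8.3.2 concerns events where "they may jeopardize the participant and may require medical or surgical intervention". Mild and severe in 8.3.3.1 are defined by effect on daily activities. Sections 8.3.1 to 8.3.7 do not name the infant.

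**What is asked, and when.** The Surveys part of 8.1 gives the general topics as feeding and contraception. Only the longer week-8 questionnaire adds "infant health and well-being, and any new pregnancies and respective pregnancy outcomes if available". The infant comes to one in-person visit, at 4 weeks (8.1, breastmilk collection), and section 3 sets infant growth as change from baseline to 4 weeks.

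**What is reported.** Under 9.4.4, events are recorded as the team learns of them. The table holds AEs that lead to stopping the intervention and serious treatment-emergent AEs. No infant row is specified. There is no DSMB (8.2), and the PI oversees safety (10.1.3).

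**The concern.** Infant exposure is one of the questions the trial exists to inform, yet the safety procedures are written around an adult participant. Staff following section 8.3 have no instruction to ask about the infant, no infant baseline for deciding what counts as a new event, and severity grades that do not fit a newborn. The enrolment questionnaire collects birth data and any intensive care stay, but no rule makes these the infant's AE baseline.

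Two things are at stake. An infant event could come to light weeks late in a trial with no independent safety review. And infant events logged at staff discretion would leave a safety record that is hard to interpret, in a pilot meant to inform a larger trial.

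**Working it through.** The plan states no figure on this point, so there is none to reproduce. The check is a comparison of sections plus day counts.

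**Inputs**
- Study pills start 120-168 hours after delivery, i.e. day 5-7 (8.1, Randomization). Section 6.1 gives 120-160 hours; 160/24 = 6.7 days, inside the same range, so the counts below do not depend on which is used.
- In-person visit with the infant at 4 weeks, taken as day 28. No visit window is given, so this is an assumption.
- Week-8 questionnaire at the end of week 8, taken as day 56.
- Surveys at the end of weeks 2, 3, 5, 6 and 7 (text link), week 4 (in person) and week 8 (email): 5 + 1 + 1 = 7.
- Group 3: placebo for 28 days, then active d-POPs at 28-35 days after delivery (8.1).
- 10 infants per arm, 30 in all (6.1).

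**Survey coverage.** Infant health is a listed topic in 1 of 7 surveys.

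**Gap from pill start, if the 4-week AE inquiry is read to cover the infant**
- Pill start to visit: 28 - 7 = 21 to 28 - 5 = 23 days.
- Visit to week-8 item: 56 - 28 = 28 days.

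**Gap from pill start, if it is not so read**
- Pill start to week-8 item: 56 - 7 = 49 to 56 - 5 = 51 days.

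**Group 3.** Active pills start on day 28-35. If the packs are taken in the order dispensed, with the 28-day placebo pack begun on day 5-7, the active pack begins on day 5 + 28 = 33 to 7 + 28 = 35, after a visit held on day 28. Growth measurement also ends at 4 weeks. From an active start on day 28-35 to the week-8 item is 56 - 35 = 21 to 56 - 28 = 28 days, with no other scheduled infant-health inquiry after the visit.

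**Context: how much one event weighs.** With no event among n infants, the one-sided 95% exact upper bound on the true rate is 1 - 0.05^(1/n).
- n = 10: 25.9%
- n = 30: 9.5%

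The chance of at least one event in an arm of 10 is 1 - (1 - p)^10. For assumed true rates of 5% and 10% this is 40% and 65%. An arm will yield few events at best, so missing one changes what the pilot can say.

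**The case against.** The strongest reply is that the infant is unnamed rather than excluded. Most of that stands.

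- The AE definition in 8.3.1 refers to humans generally. The main seriousness outcomes in 8.3.2, hospitalization among them, are not tied to the participant; that word appears only in the separate important-medical-event clause.
- Section 8.3.4 requires all AEs on study to be documented, and 8.3.5 and 8.3.6 send all AEs and SAEs to the IRB.
- Unanticipated problems (8.4.1) extend to people other than participants, although only for events that are unexpected, at least possibly related, and suggestive of greater risk.
- The 9.4.4 table is not limited to mothers.
- A mother can tell the team about her baby at any time, and weekly data on supplementation and perceived milk supply (section 3) give indirect signals.
- Only survey topics are described. The instruments themselves are not in the document and may ask more.

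A reader might go further and infer that infants fall outside the AE procedures, that their events cannot reach a safety table, or that an admission for poor weight gain in week 3 would first be heard of at week 8. The documents do not support this. The infant is present at the 4-week visit, growth is due to be measured, and AEs are asked about there, so such an admission would very likely surface. A reader might also infer that the infant stands to gain nothing. Section 2.1 expects wider contraceptive choice to lower infant as well as maternal morbidity, so the point does not rest on that.

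What the reply does not show is any sentence requiring infant events to be sought, graded or tabulated. A non-serious infant event would enter the table only if it led to stopping the pills.

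**Conclusion.** The concern holds as a gap in what is required. Infant events can be collected and reported under the current text, but nothing clearly obliges the site to do so. The severity wording does not suit a newborn, and infant health is a listed survey topic once.

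The size depends on how the 4-week AE inquiry is read: gaps of 21-23 and then 28 days if it covers the infant, and one gap of 49-51 days if it does not. Either way the interval is weeks. For Group 3, the week-8 item is in practice the only scheduled infant-health inquiry during active exposure.

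These figures assume a visit at day 28, a questionnaire at day 56, and surveys that contain only the topics described. The change is worth making because it alters the safety data collected at very little cost. The trial's primary comparison is not affected.

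**What to change.** 1. In 8.3.1 to 8.3.6, state that AE and SAE definitions, collection and IRB reporting apply to both mother and infant. Add severity wording that can be used for a newborn, for example based on unscheduled medical contact, treatment or admission.
2. Add one infant-health item (illness, unscheduled care, admission) to the existing week 2-7 surveys, including the in-person week-4 survey. State that the AE inquiry at the 4-week visit covers the infant.
3. In 9.4.4, show infant events in separate rows of the safety table.

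The cost is protocol wording and one question on surveys already being sent. No visit is added, and arms and sample size do not change. The downside is slightly longer surveys and more common newborn complaints to log.

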#### 8.3.5 ADVERSE EVENT REPORTING

All adverse events will be reported to the UCSD IRB. The management of information that is relevant to the protection of participants including adverse events, UPRs, protocol violations/ deviations, interim results and protocol modifications will be the responsibility of the PI.

#### 8.3.6 SERIOUS ADVERSE EVENT REPORTING

All serious adverse events will be reported to the UCSD IRB. The management of information that is relevant to the protection of participants including adverse events, UPRs, protocol violations/ deviations, interim results and protocol modifications will be the responsibility of the PI.

### 8.3.7 REPORTING EVENTS TO PARTICIPANTS

The UCSD IRB provide guidance to the PI on informing participants regarding AEs and SAEs as needed.

## 8.4 UNANTICIPATED PROBLEMS

### 8.4.1 DEFINITION OF UNANTICIPATED PROBLEMS (UP)

Unanticipated problems involving risks to participants or others to include, in general, any incident, experience, or outcome that meets all of the following criteria:

- Unexpected in terms of nature, severity, or frequency given (a) the research procedures that are described in the protocol-related documents, such as the Institutional Review Board (IRB)-approved research protocol and informed consent document; and (b) the characteristics of the participant population being studied;
- Related or possibly related to participation in the research (“possibly related” means there is a reasonable possibility that the incident, experience, or outcome may have been caused by the procedures involved in the research); and
- Suggests that the research places participants or others at a greater risk of harm (including physical, psychological, economic, or social harm) than was previously known or recognized.

